4.8 Safety Analysis

All safety variables will be summarised overall and by treatment group using the Safety Population.

The safety variables are:

- AEs;
- Spirometry results;
- CCI [REDACTED];
- Vital signs;
- Physical examination results;
- Haematology and clinical chemistry parameters;
- 12-lead ECG parameters.

4.8.1 Adverse Events

An AE is "any untoward medical occurrence in a subject or clinical trial subject administered a medicinal product and which does not necessarily have a causal relationship with this treatment".

An AE will be regarded as treatment-emergent if it has an onset date on or after the date of first IMP dose. For AEs with onset date on day of first IMP dose, the variable "Prior to first IMP administration?" in the Adverse Events eCRF form will be considered. AEs prior to first IMP

CONFIDENTIAL

Sponsor:	Zambon S.p.A.	Protocol Number:	Z7224L01
----------	---------------	------------------	----------

administration will be considered as non-treatment-emergent. All other AEs, i.e. AEs with negative or missing answers to the question “Prior to first IMP administration?” will be considered as TEAEs. Partially missing dates will be handled as outlined in [Section 4.11](#). If an AE has a partial or fully missing date, and it is unclear whether the AE is treatment-emergent, it will be assumed that it is.

Only TEAEs will be included in the AE and SAE summaries. Non-treatment-emergent events will be included in the subject listings and flagged but not included in the summaries.

A summary table will present the number and percentage of subjects reporting:

- Any TEAEs;
- Any TEAEs by severity;
- Any TEAEs by relationship to IMP;
- Any TEAEs by action taken with IMP;
- Any Serious TEAEs;
- Any Fatal TEAEs.

The number of events occurring will also be reported.

Related AEs are those events for which there is a reasonable possibility that the IMP caused the event. When relationship to IMP is missing for a TEAE it will be imputed to be drug-related. Every effort should be made to query the site for complete data entry prior to database lock.

Fatal AEs are those reported with an outcome of “Fatal”.

The number (and percentage) of subjects experiencing at least one TEAE, along with the number of events occurring, will be summarised by MedDRA SOC and PT, overall and by maximum severity.

A subject with more than one occurrence of the same AE in a particular SOC or PT will be counted only once in the total of those experiencing AEs in that particular SOC or PT. Two AEs with the same SOC or PT will be considered as two different events when calculating the “number of events” in the tables.

For summaries by maximum severity, if a subject experiences more than one event in the same SOC and PT, the subject will be counted in the maximum severity but all the events will be reported in their severity level. Maximum severity will be ranked as follows: severe > moderate > mild > unknown.

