Resolution of a NCFB pulmonary exacerbation is defined as the date of completion of the required course of systemic antibiotic treatment or the Investigator's judgement that the NCFB pulmonary exacerbation has resolved, whichever is later. Exacerbations occurring less than 14 days after the end of a course of systemic antibiotics for a NCFB pulmonary exacerbation will be considered as a single event (see [Section 9.1.5](#)).

IMP administration may be temporarily interrupted during the time of systemic antibiotic treatment due to a pulmonary exacerbation based on the Investigator's judgement; thereafter, the study treatment should restart as soon as possible. Stop date and re-start

date will be recorded in the relevant eCRF. The occurrence of a pulmonary exacerbation does not mandate the discontinuation of the subject from the trial, unless it occurs between Visit 1 and Visit 2 and /or the Investigator believes discontinuation is in the subject's best interest.

The following assessment will be performed at an Exacerbation Visit or Phone contact, and all details of the pulmonary exacerbation have to be recorded:

- start date and duration of all symptoms since the start;
- all symptoms present which support the NCFB pulmonary exacerbation diagnosis;
- all concomitant medications, especially systemic antibiotics;
- physical examinations and vital signs (if attending the clinic);
- date of CCI [REDACTED] and/or days of CCI [REDACTED] (if any);
- measurement and recording of FEV₁ and FVC (if feasible);
- pulmonary exacerbation as AE/SAE according to protocol and followed until resolution, including weekly follow-up phone calls as detailed above;
- collection of CCI [REDACTED] for other antibacterial panels. If subjects are unable to attend the clinic then suitable arrangements will be made to obtain an additional CCI [REDACTED], if feasible.

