9.1.6. SAFETY EVALUATIONS

Adverse Events

AEs will be recorded by the Investigator in the appropriate eCRF Section starting with the date of informed consent until the follow-up phone call. At each contact (i.e. clinical visit or phone call), subjects will be asked in a non-leading manner if they experienced any AEs.

All AEs occurring from the day of the first IMP administration, i.e. Visit 2, until the end of the trial, i.e. follow-up phone call, will be considered as TEAEs.

(Note: A pulmonary exacerbation will be reported as an AE or serious AE [SAE]; pulmonary exacerbations will also be captured as efficacy assessments).

For definitions and reporting of AEs and SAEs, see [Section 16](#).

Lung Function by Means of Spirometry

Spirometry measurements of FEV₁ and FVC (predicted values will be as per GLI reference equations [23]) will be performed at Visit 1 (if not performed in the preceding 30 days) to verify the eligibility of the subject (see inclusion criteria in [Section 7.2.1](#)), and at Visit 2 through Visit 7.

Lung function measurement and daily calibration of the spirometer will be performed according to the standardised methods described by the American Thoracic Society/European Respiratory Society. It is suggested that, in each centre, the model of the spirometer used does not change during the study.

Lung function measurements will be done at approximately the same time of the day during clinic visits (dependent on IMP administration) with subjects either standing or sitting (for each subject, this should be consistent throughout the trial) with the nose clipped after at least 10 minutes rest. Calibration of the spirometer must be performed preferably by the same Investigator at each visit prior to spirometry measurements and the reports must be kept with the source trial documents.

For FEV₁ and FVC the highest value from 3 technically satisfactory attempts will be considered (irrespective of the curve they come from).

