A fully blinded reassessment of trial size and power was undertaken for Promis I based on blinded data as of 15th January 2020 in 342 randomised, ITT population subjects. This evaluation gave a blinded annualised exacerbation rate estimate of 1.024 per year and an over-dispersion estimate of 0.273. For the hypothesised [CCI] reduction in the exacerbation rate with colistimethate sodium, this translates to annual event rate estimates for placebo and colistimethate sodium of 1.2701 vs 0.8256. The current data in Promis I, therefore, suggested that $n=145$ subjects per arm (290 total, unadjusted for dropout) were required to deliver 90% power, as compared to $n=170$ subjects per arm (340 total, unadjusted for dropout) stated in the protocol. Furthermore, the smallest observed reduction in the exacerbation rate with colistimethate sodium that will yield [CCI] in Promis I was computed to be [CCI].

This recalculation of the sample size was further refined to allow for a reduced overall exposure in Promis I arising due to some subjects dropping out of the study before completing 1 year of follow-up. This leads to a requirement for $n=188$ subjects per arm (376 total, adjusted for dropout) to detect a [CCI] reduction in the event rate with 90% power as compared to $n=210$ subjects per arm (420 total, adjusted for dropout) stated in the protocol; and with $n=188$ subjects per arm, the smallest observed rate reduction to yield [CCI] was computed to be [CCI].

It was, therefore, clear from the blinded data accrued in Promis I subjects to January 2020 that the $n=210$ subjects per arm stated in the protocol was unnecessarily high. At worst, the actual number of subjects required in Promis I is $n=188$ per arm (376 total) and this is inclusive of adjustment for the actual dropout rate seen in the trial itself. Given that, at the time of this sample size reassessment, a total of $n=372$ subjects had been randomised into Promis I, it could very reasonably be argued that very few, if any, further subjects were actually required to be randomised into the study to provide the required power to test the hypothesis that inhaled colistimethate sodium significantly reduces the exacerbation rate relative to placebo. Recruitment was, therefore, concluded with 377 randomised subjects.

CONFIDENTIAL

Sponsor:	Zambon S.p.A.	Protocol Number:	Z7224L01
----------	---------------	------------------	----------

4 Statistical Methodology

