In the case of a partial onset date of NCFB pulmonary exacerbation due to missing day, the onset of the event will be assumed to be the first day of the month. If the resultant derived date is prior to the date of first IMP dose, then it will be assumed to be equal to the first IMP dose date. Resultant derived dates will be reviewed during the blind review meeting and documented in the Blind Data Review and Analysis Sets Report.

In case of a partial resolution date of NCFB pulmonary exacerbation due to missing day, the resolution of the event will be assumed to be the last day of the month. If the resultant derived date is after the treatment completion/discontinuation date, then it will be assumed to be equal to the treatment completion/discontinuation date.

In case a NCFB pulmonary exacerbation presents a symptom with missing duration, following a conservative approach, the longest duration based on the start and stop dates of that symptom and until the resolution date of the NCFB pulmonary exacerbation will be imputed.

Two NCFB pulmonary exacerbations will be considered as a single episode in the statistical analysis if the second exacerbation started less than 14 days after the end of the systemic antibiotic therapy for the previous exacerbation (start date of the exacerbation - end date of the treatment of the previous exacerbation < 14 days). In case of more than two exacerbations for the same subject, this rule will be applied iteratively (therefore, more than two exacerbations may be considered as a single episode). Such cases will be discussed during the blind review of the data and the decisions taken will be documented in the Blind Data Review and Analysis Sets Report.

The above rule will not apply to the analysis of NCFB pulmonary exacerbations as AEs in the safety analysis.

In case of NCFB pulmonary exacerbations considered as a single episode:

- the start date of the first event will be considered as the start date;
- the stop date of the last event will be considered as the stop date;
- a worst case approach will be considered for duration of symptoms and requirement of hospitalisation. For example, if one of two exacerbations considered as a single episode has/have increased dyspnoea for ≥ 24 hours and < 48 hours and the other one has increased dyspnoea for ≥ 48 hours, the single episode will be considered in the analysis as having dyspnoea for ≥ 48 hours.

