4.7.4.1 CCI Analysis Using Alternative Definition of NCFB Pulmonary Exacerbation

A CCI analysis will be conducted using an alternative definition of NCFB pulmonary exacerbation for the mITT Population. The re-classification of pulmonary exacerbations will be done during the blind review meeting and documented in the Blind Data Review and Analysis Set Report.

In this CCI analysis, a NCFB pulmonary exacerbation is defined as deterioration in three or more of the following key symptoms for at least 48 hours:

- Cough;
- Sputum volume and/or consistency;

CONFIDENTIAL

Sponsor:	Zambon S.p.A.	Protocol Number:	Z7224L01
----------	---------------	------------------	----------

- Sputum purulence;
- Breathlessness and/or exercise tolerance (dyspnoea);
- Fatigue and/or malaise;
- Haemoptysis;

And:

a physician determines a change in bronchiectasis treatment is required when other potential causes of clinical deterioration have been discounted, i.e. the subject requires a systemic antibiotic therapy due to the NCFB pulmonary exacerbation.

Subjects experiencing NCFB pulmonary exacerbations according to this alternative definition will be identified as those subjects having:

- An AE on the eCRF Adverse Events form with a MedDRA coded Preferred Term of “infective exacerbation of bronchiectasis” that is at least 48 hours in duration (i.e. stop date of AE – start date of AE + 1 \geq 2);
- At least 3 of the above symptoms on the eCRF Pulmonary Exacerbation Symptoms form for the Pulmonary Exacerbation Number corresponding to that AE, where those symptoms all occur between the start and stop dates of the AE;
- At least 1 therapy on the eCRF Systemic Antibiotic Therapy form for the Pulmonary Exacerbation Number corresponding to that AE.

Analysis will be conducted following the same rules and methods as detailed above for the main definition of NCFB pulmonary exacerbations.

4.7.4.2 **CCI** Analysis for Discontinuers

In order to assess the potential impact of missing data on the results of the primary efficacy analysis, **CCI** analyses based on multiple imputation (MI) will be performed on all mITT subjects based on the approach proposed by Keene et al. ^[1].

For all subjects with a follow-up duration shorter than 365 days (i.e., 52 weeks + 1 day), the number of pulmonary exacerbations from the end of the follow-up period up to day 365 will be imputed.

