4.8.1.1 Subsets

- Separate summary tables by SOC and PT will be presented for treatment-emergent SAEs.
- Separate summary tables by SOC and PT and by SOC, PT and maximum severity will be presented for related TEAEs.
- Separate summary tables by SOC and PT will be presented for treatment-emergent related SAEs.

CONFIDENTIAL

Sponsor:	Zambon S.p.A.	Protocol Number:	Z7224L01
----------	---------------	------------------	----------

- Separate summary tables by SOC and PT will be presented for treatment-emergent AEs leading to the permanent discontinuation of IMP. An AE leading to discontinuation is an AE with action taken with IMP equal to "Permanently discontinued".
- Separate summary tables by SOC and PT will be presented for treatment-emergent fatal SAEs.
- Treatment-emergent SAEs and fatal AEs will be listed separately.
- The most frequent MedDRA PTs ($\geq 5\%$ of subjects with events in any treatment group) will be presented overall and by treatment. PTs will be used for tabulation, sorted by decreasing overall frequency.

All other information collected will be listed, as appropriate. Additionally, listings will display relative day of AE onset.

The relative day of AE onset will be calculated as follows:

- For pre-treatment AEs:
 - AE onset date - date of first IMP dose (if AE onset date is completely known);
 - missing (if AE onset date is incomplete or unknown).
- For TEAEs:
 - AE onset date - date of first IMP dose +1 (if AE onset date is completely known);
 - missing (if AE onset date is incomplete or unknown).

Notes:

- AEs will be coded using MedDRA version 19.1 or higher (please refer to the final Data Management Plan for the latest coding information).
- Terms will be displayed in descending overall frequency (and then alphabetically) of SOC and in descending overall frequency (and then alphabetically) of PTs within each SOC.

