5.3.4 Section 14.3: Safety

Table 14.3.1.1	Summary of Treatment Emergent Adverse Events	(Safety Population)
Table 14.3.1.2.1	Treatment Emergent Adverse Events by System Organ Class and Preferred Term	(Safety Population)
Table 14.3.1.2.2	Serious Treatment Emergent Adverse Events by System Organ Class and Preferred Term	(Safety Population)
Table 14.3.1.2.3	Related Treatment Emergent Adverse Events by System Organ Class and Preferred Term	(Safety Population)
Table 14.3.1.2.4	Serious Related Treatment Emergent Adverse Events by System Organ Class and Preferred Term	(Safety Population)
Table 14.3.1.2.5	Treatment Emergent Adverse Events Leading to Permanent IMP Discontinuation by System Organ Class and Preferred Term	(Safety Population)
Table 14.3.1.2.6	Fatal Treatment Emergent Adverse Events by System Organ Class and Preferred Term	(Safety Population)
Table 14.3.1.3.1	Treatment Emergent Adverse Events by System Organ Class, Preferred Term and Maximum Severity	(Safety Population)
Table 14.3.1.3.2	Related Treatment Emergent Adverse Events by System Organ Class, Preferred Term and Maximum Severity	(Safety Population)

CONFIDENTIAL

Sponsor:	Zambon S.p.A.	Protocol Number:	Z7224L01
----------	---------------	------------------	----------

Table 14.3.1.4	Most Frequent Treatment Emergent Adverse Events by Preferred Term ($\geq 5\%$ of Subjects with Events in Any Group)	(Safety Population)
Table 14.3.2.1	Listing of Adverse Events Leading to Death	
Table 14.3.2.2	Listing of Serious Adverse Events	
Table 14.3.2.3	Listing of Adverse Events Leading to Discontinuation of Study Treatment	
Please Note: Section 14.3.3 (Narratives of Deaths, Other Serious and Certain Other Significant Adverse Events) is not to be used for any tables		
Table 14.3.4.1.1	Spirometry: FEV ₁ and FVC Results and Change Versus Baseline	(Safety Population)
Table 14.3.4.1.2	Spirometry: Bronchospasm following IMP Administration at Visit 7 (End of Treatment)	(Safety Population)
Table 14.3.4.2.1	Vital Signs: Results and Change Versus Baseline	(Safety Population)
Table 14.3.4.2.2	Vital Signs: Normal/Abnormal NCS/Abnormal CS Results	(Safety Population)
Table 14.3.4.2.3	Vital Signs: Shift Table	(Safety Population)
Table 14.3.4.3.1	Physical Examination: Results	(Safety Population)
Table 14.3.4.3.2	Physical Examination: Shift Table	(Safety Population)
Table 14.3.4.4.1	12-lead ECG: Results	(Safety Population)
Table 14.3.4.4.2	12-lead ECG: Shift Table	(Safety Population)

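### Low-priority presentation gap: the any, serious and by-severity TEAE subject counts include the primary efficacy event, and no planned table shows them without it

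*SAP*

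**What the plan says.** Protocol 9.1.6 records each event twice: "A pulmonary exacerbation will be reported as an AE or serious AE [SAE]; pulmonary exacerbations will also be captured as efficacy assessments". Protocol 8.7 repeats this for the exacerbation visit or contact: "pulmonary exacerbation as AE/SAE according to protocol and followed until resolution".

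SAP 4.7.4 keeps these events among the AEs. After the rule that merges episodes less than 14 days apart, it adds: "The above rule will not apply to the analysis of NCFB pulmonary exacerbations as AEs in the safety analysis". The merging is switched off for safety; the events stay in.

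SAP 4.8.1 limits the AE and SAE summaries to treatment-emergent events and sets no other filter. It then says: "A summary table will present the number and percentage of subjects reporting" any TEAE, TEAEs by severity, by relationship and by action taken, serious TEAEs and fatal TEAEs.

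The subsets in SAP 4.8.1.1 and the table index in SAP 5.3.4 cover serious, related, serious related, discontinuation, fatal, maximum-severity and most-frequent-term tables. Examples are "Serious Treatment Emergent Adverse Events by System Organ Class and Preferred Term" and "Separate summary tables by SOC and PT and by SOC, PT and maximum severity will be presented for related TEAEs". No title excludes exacerbations. The SAP Addendum and the later note to file add efficacy outputs only.

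On the efficacy side, SAP 4.7.4 plans by-arm counts of subjects with any, severe and non-severe exacerbations (Tables 14.2.1.1.1 and 14.2.1.2.1).

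**The concern.** If the drug works, fewer active subjects have an exacerbation, so fewer enter the any, serious and severe TEAE counts on that account. The fall reflects efficacy, but it appears in the headline safety rows, where it can offset an excess of other events.

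The exacerbation term has its own row (SAP 4.7.4.1 names the preferred term "infective exacerbation of bronchiectasis"), but subtracting that row does not solve the problem. Each subject is counted once, and a subject with an exacerbation is in the total whether or not something else happened. An exacerbation may also be coded elsewhere, for instance to pneumonia (SAP 4.13).

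At stake is how a benefit-risk reader interprets three headline contrasts and one SOC total. The SAP Addendum (section 3) has in view a regulatory application resting on a single pivotal study, where such a reader would want benefit and harm shown apart.

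**Working it through.** **Inputs.** SAP 3.9 gives annual rates of 1.2701 (placebo) and 0.8256 (active) and over-dispersion k = 0.273. The rate of other TEAEs, b, is not in the documents. It is assumed to be 50%, with 80% as a variant, and independent of exacerbations.

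**Check of the inputs against the plan's own figure.** n per arm = (1.960 + 1.282)² × [1/1.2701 + 1/0.8256 + 2 × 0.273] / ln(0.650)² = 10.507 × 2.5446 / 0.18554 = 144.1, which rounds up to the SAP's 145.

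**Subjects with at least one exacerbation, one year for everyone.** P = 1 − (1 + k × rate)^(−1/k).
- Placebo: 1 − 1.34674^(−3.663) = 0.6639
- Active: 1 − 1.22539^(−3.663) = 0.5250

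**Any TEAE** = 1 − (1 − P)(1 − b).
- Equal harm, b = 50%: placebo 1 − 0.3361 × 0.5 = 83.2%; active 1 − 0.4750 × 0.5 = 76.3%. The difference is 6.9 points favouring active.
- Excess on active that is fully offset: (1 − b) × [1 − 0.3361/0.4750] = 0.5 × 0.2924 = 14.6 points.
- A 10-point excess at b = 50%: active 1 − 0.4750 × 0.4 = 81.0% against 83.2%, so 2.2 points lower on active.
- A 10-point excess at b = 80%: active 1 − 0.4750 × 0.1 = 95.2% against 1 − 0.3361 × 0.2 = 93.3%, so 2.0 points higher (unrounded), diluted but visible.
- Background above which a 10-point excess is no longer reversed: 1 − 0.10/0.2924 = 66%.

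**Allowing for dropout.** SAP 3.9 refined its calculation to "allow for a reduced overall exposure in Promis I arising due to some subjects dropping out of the study" early, but does not give its formula, so two patterns are assumed. In each, a fraction c completes one year and the rest leave uniformly over it. For those who leave, the mean P is 1 − [1 − (1 + k × rate)^(1 − 1/k)] / [rate × (1 − k)], which is 0.4072 on placebo and 0.3036 on active.
- c = 0.80 (the protocol's 20% withdrawal): placebo 0.8 × 0.6639 + 0.2 × 0.4072 = 61.3%; active 0.8 × 0.5250 + 0.2 × 0.3036 = 48.1%. Full offset at b = 50%: 0.5 × (1 − 0.3874/0.5192) = 12.7 points. Reversal threshold: 61%.
- c = 0.44: the sample size formula with its rate terms divided by mean exposure returns the SAP's 188 per arm at 0.7206 year, and c + (1 − c)/2 = 0.7206 gives c = 0.4412. Placebo 52.0%, active 40.1%. Full offset: 0.5 × (1 − 0.4795/0.5987) = 10.0 points. Reversal threshold: 50%.

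**Sensitivity (full year, b = 50%).** A shared gamma frailty in place of independence gives a full offset of 14.8 points. A 20% rate reduction (1.145 against 0.916, same geometric mean of 1.024) gives 8.2. No drug effect gives 0.

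**What subtraction can recover.** In the equal-harm case, any TEAE minus any exacerbation is about 17% on placebo and 24% on active, although the true non-exacerbation rate is 50% in both. These are only lower bounds; the any-TEAE count is the upper bound.

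**The case against.** The plan is consistent with itself. Protocol 16.1 counts deterioration from the primary illness as an AE, and Protocol 16.3.1 declares exacerbations, including pneumonia, to be expected. Showing all TEAEs applies that definition, and leaving out investigator-reported AEs could hide worsening of the target disease. This stands, and it is why the all-TEAE tables should remain the main ones.

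The plan also supplies mitigations. Tables 14.2.1.1.1 and 14.2.1.2.1 show by arm how many subjects had any, severe and non-severe exacerbations. Listing 16.2.7.1 covers all AEs and Listings 16.2.7.4.1 and 16.2.7.4.2 the exacerbations, so any, serious and severe counts could be tallied by hand. This also stands: a reader can see how large the masking might be. What is missing is the exact subject count by arm. Severe in Table 14.2.1.2.1 means intravenous antibiotics or hospitalisation, which is neither the AE severity grade nor seriousness. The table shells are a separate document, not available here, and may contain more.

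A reader might infer that the safety analysis is wrong, or that it would hide a harm signal. The documents do not support either reading. No test, margin or numerical stopping rule uses these counts; Protocol 15 leaves stopping to sponsor judgement. Other preferred-term rows, other SOC totals, non-exacerbation event counts (by subtraction), the related and discontinuation tables and the bronchospasm analysis are largely unaffected.

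**Conclusion.** The gap is real but narrow. Three subject-level counts (any, serious and by-severity TEAEs) and one SOC total contain the primary efficacy event, and no planned table gives them without it.

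At the SAP 3.9 rates and a 50% background, the true excess that would be fully offset is about 14.6 points with complete follow-up, and about 10 to 13 points depending on the dropout pattern assumed. It would be tempting to say that a real excess would appear as a benefit. For a 10-point excess that holds only while the background is below roughly 50% to 66%; above that the excess is diluted, not reversed.

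The sizes rest on the hypothesised 35% rate reduction and on an assumed background, held constant across follow-up patterns and independent of exacerbations. The documents give no serious or severe share of exacerbations, so no size is put on those two counts. This is a presentation improvement of low priority.

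**What to change.** Keep the all-TEAE tables as the main ones. SAP v2.0 is final and the study is unblinded (SAP Addendum 2.2), so add one companion set through a further addendum and label it post hoc:

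- Number and percentage of subjects with any, serious and severe TEAEs, by arm, overall and by SOC and PT.
- Exclude AEs linked through the eCRF AE number (SAP 4.5.5) to exacerbations finally classed as meeting the protocol-defined criteria. Apply this to each AE, before the 14-day merge.
- Retain AEs with preferred term Pneumonia, episodes that did not meet the criteria and exacerbations judged related to study drug, so that possible harm is not filtered out.
- Add a footnote that some efficacy effect may remain, because Protocol 8.7 treats pneumonia as a severe exacerbation and non-qualifying episodes may also be fewer on active.

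Leave the related and discontinuation tables and Protocol 15 unchanged. The cost is one filter on an existing link and one extra set of AE tables; no new data are needed.
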